1. 32. Glossary Contents 43. Signature page 54. Summary and synopsis Introduction 75.1 Background 65. Preclinical data 85.3 Clinical data 95.4 85.2 Rationale 105.5 Risks / benefits 106. Study objectives 106.1 Primary objective 106.2 Secondary objectives 106.3 Primary endpoint 106.4 Secondary endpoint 107. Study population 117.1 Inclusion criteria 117.2 Exclusion criteria 118. Study design 119. Study procedures 1210. Assessment and management of risk 1311. Statistical considerations 1311.1 Sample size 1311.2 Method of analysis 1312. Ethics 1413. Public Involvement 1414. Data handling and record keeping 1514.2 Source data 1514.1 Data management 1514.3 Confidentiality 1515. Interventions and tools 1514.4 Record Retention and Archiving 1515.1 Devices 1515.2 Tools 1616. Safety reporting 1616.1 Adverse Events (AEs)1616.2 Adverse Reaction (ARs) 1616.3 Notification and reporting of Adverse Events and Reactions 1616.4 Serious Adverse Events (SAEs) or reactions 1616.5 Notification and reporting of Serious Adverse Events 1716.7 Annual Safety Reporting 1716.6 Urgent Safety Measures 1716.8 Overview of the Safety Reporting responsibilities 1717. Monitoring 1819. Finance and funding 1820. and auditing 1718. Trial committees Indemnity 1821. Dissemination of research findings 1822. References 18

2. Glossary

MVA	Manual vacuum aspiration
SMM	Surgical management of miscarriage
VR	Virtual Reality

KEYWORDS

Distraction techniques

Acute pain

Anxiety

Manual vacuum aspiration

Virtual reality

3. Signature page

Chief Investigator Agreement

The study as detailed within this research protocol will be conducted in accordance with the principles of Good Clinical Practice, the UK Policy Framework for Health and Social Care Research, and the Declaration of Helsinki and any other applicable regulations. I agree to take responsibility for the statistical analysis and oversight of this study.

Signature:

Date:

4. Summary and synopsis

Short title	Virtual Reality in Manual Vacuum Aspiration
Methodology	Prospective feasibility study
Research sites	Whipps Cross Hospital, Barts Health NHS Trust
	North Middlesex University Hospital NHS Trust
Objectives / aims	To study the feasibility of using virtual reality as a
	distraction technique for the management of acute pain
	and anxiety during manual vacuum aspiration for
	miscarriage
Number of	30
participants	
Inclusion and	Women aged 18-50 undergoing manual vacuum
exclusion criteria	aspiration
Statistical	Qualitative and quantitative data analysis
methodology and	 Patient questionnaire
analysis (if	Staff questionnaire
applicable)	 Semi-structured patient interview.
Study duration	6 months

5. Introduction

5.1 Background

Many simple gynaecological procedures can be performed in an outpatient setting without the need for general anaesthesia. Such office-based procedures include outpatient hysteroscopy, endometrial biopsy, large-loopexcision of the transformation zone and manual vacuum aspiration for the management of miscarriage. Advantages experienced by patients include reduced anaesthetic risk, enhanced recovery time and flexibility of timings. For the healthcare provider there are significant cost benefits on the basis of reduced theatre time, staff and equipment. Patient satisfaction is generally high but influenced by their experience of pain and feelings of anxiety before, during and after the procedure.

5.2 Preclinical data

Approximately one in four pregnancies end in miscarriage with early pregnancy loss accounting for 50,000 hospital admissions a year ¹. Treatment options include expectant, medical and surgical management with patient preference and clinical suitability the key determinants. The standard option for surgical management of miscarriage (SMM) involves suction curettage under general anaesthesia. In keeping with guidance from the National Institute of Health and Care Excellence (NICE) many hospitals now also offer manual vacuum aspiration (MVA) using a handheld syringe under local anaesthesia as a safe and efficacious alternative ¹. Although there are no national guidelines as to those patients suitable for MVA the widely accepted consensus excludes women who are haemodynamically unstable, those with bleeding disorders and uterine malformations and those with retained products of conception greater than 5cm or signs of infection². As with SMM, risks include uterine and cervical injury, pelvic infection, incomplete evacuation and uterine perforation. However, as most practitioners carry out the procedure under ultrasound guidance, the safety profile with regards to perforation and need for repeat procedure are favourable².

Like many office gynaecology procedures, MVA involves the insertion of a speculum, a degree of cervical dilatation and subsequent uterine intervention and therefore has the potential to act as a noxious stimulus at the levels of the vulva, vagina, cervix and uterus. Innervation of the uterine body is by sympathetic fibres arising from T10-L1 spinal segments, which course through the uterosacral ligaments via the inferior hypogastric nerve and ovarian plexus. The lower uterine segment, cervix and upper vagina are innervated by parasympathetic fibres arising from S2-4 whilst the pudendal nerve arising from S2-4 innervates the lower vagina and vulva.

One of the biggest challenges to patient acceptability of MVA is adequate pain relief during and after the procedure. The degree of pain experienced varies considerably from no pain to significant pain². A woman's anxiety level strongly influences her perception of pain and at the time of miscarriage most women will experience a period of intense emotional distress. Comfort can be improved by the use of a suitable procedure room; kind, empathetic staff and clear

Virtual Reality in Manual Vacuum Aspiration. Version 8.0. 27/02/2021 Page 7 of 19

counselling with regards to what to expect during and post procedure. However, there is a paucity of data on interventions to reduce anxiety during MVA.

In the absence of general anaesthesia, pain management options include sedation, oral analgesics and paracervical block with local anaesthetic. Intravenous sedation is not a practical method for office gynaecology procedures, as it requires the presence of an anaesthetist for its administration and subsequent airway support. Non-steroidal-anti-inflammatory medications are effective in reduction of uterine contraction by the inhibition of cycloxeganse and reduction in circulating prostaglandins and patients undergoing MVA are recommended to take 400mg Ibuprofen 30-60 minutes prior to procedure ². Whilst many outpatient gynaecology procedures are performed following administration of a paracervical block, the infiltration will not reach the level of the uterine fundus supplied by spinal nerves T10-L1. Furthermore, a Cochrane review by Tangsirwatthana *et al* 2013 concluded that there was a lack of evidence to support the use of paracervical block for cervical dilatation and uterine intervention ³.

5.3 Clinical data

Non-pharmacological methods of pain relief include distraction techniques. These may be passive; ie, listening to music, watching television or active; i.e. interactive toys, guided relaxation and controlled breathing. Intraoperative pain and anxiety ratings have been noted to be lower by use of simple intraoperative distraction techniques e.g. interacting with nurses, watching DVDs or using stress balls ⁴. There is however, limited and conflicting evidence for the use of distraction techniques in office gynaecology.

A study by Angioli *et al* 2014, showed a significant reduction in pain and anxiety in outpatient hysteroscopy with the use of music however, a subsequent randomised controlled trial by Mak *et al*, 2017 showed no positive effect of music on patient's level of pain, anxiety or satisfaction at outpatient hysteroscopy or colposcopy ^{5,6}. Baser *et al* 2013, demonstrated women with high level pre-procedural anxiety to be more likely to perceive higher levels of pain and discomfort during colposcopy ⁷. Simple visual distraction during colposcopy has been associated with a reduction in pain score but no change in anxiety levels ⁸.

Virtual reality is a relatively new intervention, which has been utilised as a nonpharmacological method for pain relief in paediatrics, dentistry, the management of chronic pain and the treatment of burns victims ⁹. It acts as a distraction technique by giving an immersive and engaging experience, which changes the activity of the body's pain modulation system. VR distraction has been associated with significant increases in pain threshold and pain tolerance and significant decreases in pain intensity, time spent thinking about pain and self-reported anxiety relative to baseline ¹⁰. A recent meta-analysis by Mallari *et al*, 2019, supported VR as an effective treatment for reducing acute pain ¹⁰. A pilot study by Deo *et al*, 2019, showed promising results for the feasibility of immersive VR in outpatient hysteroscopy in reduction of pain and anxiety scores ¹¹.

Pain management in ambulatory procedures should be multimodal and include both pharmacological and non-pharmacological interventions. Giving patients a range of options will increase the number of successful procedures and improve patient experience.

5.4 Rationale

To study the role of distraction techniques and the feasibility of using virtual reality for the management of acute pain and anxiety experienced by patients undergoing manual vacuum aspiration.

5.5 Risks / benefits

Potential benefits to participants in the study include reduction in perceived pain, reduction in anxiety and increased tolerability of procedure. Potential risks to participants include disorientation, nausea and a sensation of motion sickness. In those with a history of epilepsy it may induce seizures ¹².

6. Study objectives

6.1 Primary objective

• Feasibility of using virtual reality as a distraction technique in management of acute pain and anxiety in patients undergoing manual vacuum aspiration for miscarriage.

6.2 Secondary objectives

- Understanding the acceptability and effectiveness of VR interventions in office gynaecology procedures
- Understanding the factors that might influence the willingness of patients to participate in a future formal trial of the technology.
- Understanding how best to implement the technology and designing of the contents of the VR intervention.

6.3 Primary endpoint

- Feasibility of using virtual reality as a distraction technique in management of acute pain and anxiety in patients undergoing manual vacuum aspiration for miscarriage.
- Recruitment and data analysis of 30 patients

6.4 Secondary endpoint

Qualitative and quantitative data from 30 patients in the form of

Virtual Reality in Manual Vacuum Aspiration. Version 8.0. 27/02/2021 Page 9 of 19

- i. Patient questionnaire
- ii. Staff questionnaire
- iii. Semi-structured patient interview (from VR group only)

7. Study population

Participants will be recruited for the study at the Gynaecology Departments at Whipps Cross University Hospital, Barts Health NHS Trust and *North Middlesex University Hospital NHS Trust* over a 6 month period. The patients will be identified from the early pregnancy unit by the clinicians who schedule them for MVA procedure. All patients undergoing MVA that fit the eligibility criteria will be invited to participate at the time of booking the procedure. The study will recruit 30 patients.

7.1 Inclusion criteria

Patients: Clinical indications for undergoing an MVA will be confirmed.

Inclusion criteria will include all women of 18 - 50 years of age, planned for a MVA who are able and willing to give informed consent.

Staff: Inclusion criteria will include the clinician performing the MVA and the nurse supporting the clinic.

7.2 Exclusion criteria

Patients:

- Hearing impairments and blindness
- History of epilepsy or any previous seizures
- History of claustrophobia
- Any known anatomical characteristics that may make performing the office procedure more difficult (e.g., cervical conisation)
- Any known characteristics that make the patient unsuitable for undergoing MVA (e.g. known bleeding disorder, gestation >12 weeks)
- The denial or withdrawal of informed consent

Staff: The denial or withdrawal of informed consent

8. Study design

The study is a prospective trial involving mixed methods of qualitative and quantitative analysis. The study will include 30 patients attending for MVA who will be offered inclusion in the study at the time of booking the procedure.

They will be given a study information sheet, an invitation to participate with a reply slip to indicate whether they would like to participate in the study. Patients will be given standard pre-procedural information about the procedure as per standard practice. Written informed consent will be obtained from participants and the interview outputs will be anonymised.

Virtual Reality in Manual Vacuum Aspiration. Version 8.0. 27/02/2021 Page 10 of 19

All patients will fill in a questionnaire before and after the procedure and the 15 patients who use the virtual reality headset will have a semi-structured interview regarding their experience. This will be audio recorded. The interview will last approximately 10 minutes.

The staff in the clinic will include a clinician performing the procedure and a staff nurse supporting the clinic to whom both will be given a study information sheet regarding the study and a written informed consent for a questionnaire will be obtained from them if they agree to participate. The clinician performing the procedure will fill in a questionnaire per patient regarding the ease of the procedure and perceived pain levels of the patient. The Clinician performing the procedure and nursing staff's perception regarding feasibility of using the VR equipment for each patient who had the intervention will also be assessed through the questionnaire.

Patient follow up will not be routinely arranged for the purpose of the study. Routine follow up as per clinical requirements will be arranged as routine for the procedure performed.

9. Study procedures

The study will recruit 30 patients to use VR during MVA. On confirmation of consent the patients will be allocated to VR intervention group or no intervention standard care for MVA control group. 15 patients will be recruited to each group across both sites. Allocation to control or intervention will be performed by computer-generated randomisation. All patients will receive the same analgesia as per standard MVA protocol using para-cervical block.

The VR intervention will involve watching a standard content of the video on a mobile device using a VR headset to distract them during the procedure. The duration of the video will be 15 minutes; but the video will only be played for the duration of the MVA. Patients are allowed to stop viewing the video if they so desire and this will be recorded. If the MVA lasts longer than the VR experience the programme can be restarted and watched again.

Patients in both groups will fill pre and post procedural questionnaires. Pain and anxiety scores prior to and after the procedure will be evaluated. Scores will be measured by a Numeric Rating Scale (NRS) which is a validated measure of pain which is easy to use, has high compliance rates and detects meaningful changes in pain ¹³.

A semi-structured interview will be conducted with the VR intervention group patients each lasting approximately 10 minutes. The semi-structured interviews will allow for participants to be asked similar questions within a flexible framework ^{14,15}. The interviews will be conducted within 30 minutes of the procedure, in a suitable location and will be recorded on a digital voice recorder. The questions will be focused on the women's experiences of the procedure, their pain perception, anxiety levels and questions around the VR intervention as well as any other aspect of their hospital care they felt to be relevant. If further clarification or exploration of any particular aspect of their care was required, the interview will readdress these topics before the end of the interview. Interviews will continue until no new information is obtained, indicating that

Virtual Reality in Manual Vacuum Aspiration. Version 8.0. 27/02/2021 Page 11 of 19

the theoretical saturation point has been reached ¹⁶.

Clinician and nursing staff's perception regarding feasibility of using the VR equipment will also be assessed through a questionnaire. The clinician questionnaire will also assess the ease of the procedure and perceived pain scores for the patient.

Patient follow up will not be routinely arranged for the purpose of the study. Routine follow up as per clinical requirements will be arranged as routine for the procedure performed.

Patients and staff can withdraw from the study if they so desire at any time and without giving a reason. A decision to withdraw at any time, or a decision not to take part, will not affect the standard of care or treatment that they receive.

The study will end once the proposed numbers of patients have been recruited and data analysis completed. Participants will be debriefed after their participation in the study and will be directed to suitable support agencies if necessary.

10. Assessment and management of risk

Possible risks of participation in the study include the potential to experience the side effects of nausea, headaches and motion sickness during the use of VR programme. Approximately 25-40% of users of VR experience these symptoms. The risks are greater with prolonged use of more than 30 minutes ¹². VR is a known trigger for seizures in those with a history of epilepsy, for this reason women with any history of seizures or epilepsy will be excluded from the study.

Participants will be informed of these risks at the time of invitation to the study and details will be included in the patient information leaflet. Any participant wishing to end the VR programme may do so at anytime and this will be recorded.

11. Statistical considerations

11.1 Sample size

The study will include 30 patients with 15 patients in the VR intervention group and 15 patients in the MVA standard care control group.

• 11.2 Method of analysis

The recruitment of women and interviewing will proceed alongside data coding and preliminary analysis.

The statistical analysis will include statistical comparison of pre and post anxiety and pain scores. Interview analysis will be performed by the chief investigator and/or study manager. Interviews will be transcribed verbatim and initially coded by reading and re reading the transcript and making notes, drawing on the observations made during the interviews and transcription. Transcripts will be coded line-by-line, describing,

Virtual Reality in Manual Vacuum Aspiration. Version 8.0. 27/02/2021 Page 12 of 19

summarising and attending to linguistic elements such as pronoun and metaphor use. The transcripts will be entered into a qualitative software package (N6) and a thematic analysis undertaken from the emergent themes developed from these codes and cluster with related themes. Initial coding is Initial phase, which involves open coding. Axial coding and selective coding with use of constant comparison will enable a cyclical and iterative process on the principles of grounded theory. Analytic frame for the analysis will be linked to the primary and secondary aims.

Staff questionnaires will be analysed to correlate pain scores of actual vs. perceived and feasibility of carrying out the intervention will be assessed.

Demographic data would include age, parity and ethnicity.

Data and all appropriate documentation will be stored for a minimum of 20 years after the completion of the study, including the follow-up period.

12. Ethics

The Chief Investigator will obtain approval from an NHS ethics committee. The Chief Investigator will require a copy of the Trust R&D approval letter before accepting participants into the study. The study will be conducted in accordance with the recommendations for physicians involved in research on human subjects adopted by the 18th World Medical Assembly, Helsinki 1964 and later revisions.

Consent

Consent to enter the study will be sought from each participant only after a full explanation has been given, an information leaflet offered and time allowed for consideration. Signed participant consent will be obtained. The right of the participant to refuse to participate without giving reasons will be respected. After the participant has entered the study the clinician remains free to give alternative treatment to that specified in the protocol at any stage if he/she feels it is in the participants' s best interest, but the reasons for doing so will be recorded. In these cases the participants remain within the study for the purposes of follow-up and data analysis. All participants are free to withdraw at any time from the protocol treatment without giving reasons and without prejudicing further treatment.

Confidentiality

Information related to participants will be kept confidential and managed in accordance with the Data Protection Act, NHS Caldecott Principles, The Research Governance Framework for Health and Social Care, and the conditions of Research Ethics Committee Approval.

Conflicts of interest The CI and PI have no conflicts of interest.

13. Public Involvement

Virtual Reality in Manual Vacuum Aspiration. Version 8.0. 27/02/2021 Page 13 of 19

The inspiration for this study was a patient's inquiry about using her own VR headset during MVA. They subsequently aided in the study design, choosing of video content and the VR device. Informal feedback from patients offered the VR device during MVA procedure include "good distraction"; "visual nature goggles helped so I didn't watch or listen" and "wouldn't want to see the procedure".

14. Data handling and record keeping

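### The trial randomises 15 women to VR and 15 to control, but the only stated analysis of patients' pain and anxiety scores is before against after, with no comparison between arms

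*Combined protocol and SAP*

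**What the plan says.** - **Design.** Section 9 (Study procedures) states: "Allocation to control or intervention will be performed by computer-generated randomisation". Sections 9 and 11.1 both give 15 patients per group.
- **Co-treatment.** Section 9 also states: "All patients will receive the same analgesia as per standard MVA protocol using para-cervical block".
- **Data.** Section 9: "Patients in both groups will fill pre and post procedural questionnaires. Pain and anxiety scores prior to and after the procedure will be evaluated". The scores are therefore planned in both arms.
- **Objective.** Section 6.2 includes: "Understanding the acceptability and effectiveness of VR interventions in office gynaecology procedures".
- **Analysis of the scores.** Section 11.2 (Method of analysis) states: "The statistical analysis will include statistical comparison of pre and post anxiety and pain scores". It names no test, no effect measure and no contrast between groups.
- **Other quantitative analysis.** Section 11.2 adds: "Staff questionnaires will be analysed to correlate pain scores of actual vs. perceived", together with a staff assessment of feasibility. The correlation sets patient ratings against staff ratings, not VR against control.
- **Endpoints.** Sections 6.3 and 6.4 list feasibility, recruitment and data sources. Neither contains a between-group contrast.

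**The concern.** The plan sets up a randomised control arm and gives it no stated part in the analysis of the patients' scores. A before/after comparison, whether made in the VR arm, in each arm or in all 30 women together, measures what happened over the course of the MVA. It does not measure what VR added. Only the difference between randomised arms removes the part of the change that both groups share.

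The error can go either way. Anxiety that falls in every woman once the procedure is finished could be credited to VR. Pain that rises because of the procedure could hide a real VR benefit. In both cases the effectiveness part of the secondary objective would rest on a contrast that cannot inform it.

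**Working it through.** **Is a between-arm comparison stated anywhere?** Sections 6.1 to 6.4, 8, 9, 11.1, 11.2 and 15.2 were read for one, as was the rest of the document. The statements on evaluating the patients' scores are the sentence in section 11.2, the sentence in section 9 and the staff correlation. None compares VR with control.

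**Why the contrast matters.** Let *c* be the mean before/after change that every woman would have without VR, and *v* the added effect of VR. The expected change is *c + v* in the VR arm and *c* in the control arm. A paired test in the VR arm tests *c + v* = 0, and the control arm's test concerns *c* alone. Pooling 15 + 15 women tests *c + v*/2 = 0. Only the difference between arms, (*c + v*) − *c* = *v*, isolates VR.

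**Inputs.** From the documents: 15 per arm and a 0 to 10 NRS. The documents give no SD, expected change, significance level or power, so there is no figure of the plan's own to reproduce. Assumed for illustration: two-sided 0.05, and an SD of change of 2, 2.5 or 3 NRS points.

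**Paired test in the VR arm when VR does nothing (*v* = 0).** The noncentrality is *c*/SD × √15 on 14 degrees of freedom, with critical value 2.145. For *c* = 1 and SD = 2 it is 0.5 × 3.873 = 1.94, which gives probability of significance *p* = 0.438. If both arms have the same *p*, the chance that VR is significant and control is not is *p*(1 − *p*), here 0.438 × 0.562 = 0.246.

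| Shared change *c* | VR arm significant, SD 2 / 2.5 / 3 | VR significant and control not, SD 2 / 2.5 / 3 |
|---|---|---|
| 1 point | 0.438 / 0.303 / 0.226 | 0.246 / 0.211 / 0.175 |
| 2 points | 0.949 / 0.821 / 0.671 | 0.048 / 0.147 / 0.221 |
| 3 points | 0.9997 / 0.991 / 0.949 | 0.0003 / 0.009 / 0.048 |

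In simulation with no VR effect and shared changes of 1 to 3 points, the between-arm t-test rejected in about 5% of trials throughout.

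**The opposite error.** Suppose the MVA raises pain by 2 points and VR removes 1 of them. The VR arm's net change is 2 − 1 = +1. By the first row of the table, its paired test would show a significant rise in pain 23% to 44% of the time, although VR had helped.

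**Precision of the contrast that is missing.** For a baseline-adjusted difference, the 95% CI half-width is t(0.975; 27) × SD × √(1 − ρ²) × √(2/15), with t = 2.052 and √(2/15) = 0.365. SD here is that of the post-procedure score and ρ is the pre/post correlation, both assumed.

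- SD 2, ρ 0.7: 2.052 × 2 × 0.714 × 0.365 = 1.07
- SD 2.5, ρ 0.5: 2.052 × 2.5 × 0.866 × 0.365 = 1.62
- SD 3, ρ 0.3: 2.052 × 3 × 0.954 × 0.365 = 2.14

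The interval would be about ±1.1 to ±2.1 points on a 0 to 10 scale. That is useful for planning a later trial but not for a conclusion on efficacy.

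**The case against.** - **The wording is open.** Section 11.2 says what the analysis will include, which does not rule out more, and a control group with questionnaires implies a comparison. The sentence might even be read as comparing pre scores and post scores between the groups. The first part stands: the control arm's role is unspecified, not excluded. The last reading is strained, and an implied analysis fixes neither the outcome form nor the use of baseline.
- **This is a mixed-methods feasibility study.** Its primary objective is untouched, and the VR-arm interviews also bear on effectiveness. That is fair, and no powered test is called for. But interviews held in one arm cannot show what would have happened without VR.
- **The percentages assume a misreading the protocol does not announce.** They apply only if a within-arm p-value is taken as evidence on VR. This stands, and they are an illustration of the risk.
- **The two sets of assumptions differ.** With equal pre and post SDs, the precision inputs imply an SD of change, SD × √(2(1 − ρ)), of 2 × √0.6 = 1.55 to 3 × √1.4 = 3.55. Over that wider range the paired test is significant about 17% to 64% of the time for a 1-point change and 53% to 99.6% for a 2-point change. The ranges widen and the conclusion is unchanged.
- **The anxiety scale.** Section 15.2 describes it only for pre-operative anxiety. Sections 9 and 11.2 nevertheless both plan anxiety scores before and after, so the proposed analysis relies on planned data.

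**Conclusion.** The concern holds and should be fixed. That no between-arm comparison of the patients' scores is stated is a matter of text and needs no assumption. That a before/after comparison cannot isolate a VR effect follows from the design. The size of the risk depends on the assumed SD of change (2 to 3 points), the assumed shared change and a two-sided 0.05 level, none of which the documents supply. The gap is confined to the effectiveness part of the secondary objective, and the missing contrast would itself be exploratory at this sample size.

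**What to change.** Add to section 11.2:

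> For pain and for anxiety separately, the post-procedure NRS will be compared between the VR and control groups as randomised, adjusted for the pre-procedure NRS, and reported as an exploratory mean difference with 95% CI. Within-group pre/post changes will be descriptive only. The study is not powered for effectiveness, and no efficacy conclusion will be drawn from p-values.

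A term for site is optional. The cost is protocol wording only: no extra patients, visits or measurements. Because section 11.2 lets preliminary analysis run alongside recruitment, the text should be in place before any scores are compared.

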15.2 Tools

- Numeric Rating Scale (NRS) is a validated measure of pain, which is easy to use, has high compliance rates and detects meaningful changes in pain. The NRS is an 11-point scale consisting of integers from 0 through 10; 0 representing "No pain" and 10 representing "worst imaginable pain." Respondents select the single number that best represents their pain intensity. Ratings of pre-operative anxiety are measured by an 11-point numeric rating scale. 'How would you rate any anxiety you may currently be feeling' 0 (no anxiety) and 10 (worst anxiety imaginable) ¹³.
- Semi structured interviews will allow for all participants to be asked similar question within a flexible framework ^{14,15}.

16. Safety reporting

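### Section 11.2 specifies no use of pre-procedure anxiety in the pain analysis, although the protocol calls anxiety a strong influence on perceived pain and scores it in both arms

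*Combined protocol and SAP*

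**What the plan says.** - **Planned analysis (Section 11.2).** "The statistical analysis will include statistical comparison of pre and post anxiety and pain scores". No model, covariate or between-arm contrast is named. The only other stated use of pain scores is a correlation of the patient's own score with the staff's perception of it. Age, parity and ethnicity are listed as demographic data, not as covariates.
- **Anxiety as a driver of pain (Sections 5.2 and 5.3).** "A woman's anxiety level strongly influences her perception of pain". A cited study is said to have shown "women with high level pre-procedural anxiety to be more likely to perceive higher levels of pain and discomfort during colposcopy".
- **What is collected (Sections 9 and 15.2).** "Pain and anxiety scores prior to and after the procedure will be evaluated", in both groups. "Ratings of pre-operative anxiety are measured by an 11-point numeric rating scale", running from 0 to 10.
- **Size and allocation (Sections 11.1 and 9).** "The study will include 30 patients with 15 patients in the VR intervention group and 15 patients in the MVA standard care control group". "Allocation to control or intervention will be performed by computer-generated randomisation". No stratification or minimisation is described, for anxiety or anything else.
- **Timing (Sections 8 and 9).** Women are allocated once consent is confirmed. The first questionnaire comes before the procedure, but no section places it before the woman knows her arm.
- **Standing of the pain data (Section 6).** The primary objective and endpoint are feasibility. Effectiveness is part of one secondary objective, and the questionnaire data are the secondary endpoint.

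**The concern.** The protocol names a baseline variable that it believes drives the pain outcome, collects it in every woman, and then specifies no use for it, either in allocation or in the pain analysis. The only baseline that Section 11.2 implies for pain is the pre-procedure pain score. That score is taken before the speculum, cervical dilatation and uterine intervention that Section 5.2 describes as the source of pain, so it need not predict procedural pain well.

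Two things are at stake in a comparison of 15 with 15. First, a chance difference in anxiety between the arms carries over in part into the pain difference. Second, if anxiety is as prognostic as the background says, leaving it out gives a wider interval than the data allow. Section 6.2 looks ahead to a future formal trial, which the pain estimate and its SD would naturally inform. Leaving the covariates open also means that they could be chosen after the scores have been seen.

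**Working it through.** **Inputs.** From the documents: 15 per arm, simple description of randomisation, 0–10 scales. Assumed, because the documents give no figure: SD of post-procedure pain 2.5 (range 2 to 3), SD of pre-procedure anxiety 2.5, and a range for r, the correlation of pre-procedure anxiety with post-procedure pain.

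**1. The plan's own figure.** The total of 30 cannot be reproduced: Section 11.1 gives no alpha, power, effect or SD. For context, with an assumed two-sided alpha of 0.05 and 80% power, 15 per arm detects (1.960 + 0.842) × √(2/15) = 1.02 SD.

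**2. Chance imbalance in anxiety.** The SD of the difference in arm means is 2.5 × √(2/15) = 2.5 × 0.365 = 0.913 points. P(difference of at least 1 point, either direction) = 2 × [1 − Φ(1/0.913)] = 2 × [1 − Φ(1.095)] = 0.27.

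**3. Effect of an imbalance on pain.** Expected shift = imbalance × r × (SD of pain / SD of anxiety). With equal SDs, a 1-point imbalance shifts the pain difference by 0.3 points at r = 0.3, 0.5 at r = 0.5 and 0.6 at r = 0.6.

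**4. Interval without adjustment.** Half-width = t(0.975, 28) × SD × √(2/15) = 2.048 × 2.5 × 0.365 = 1.87 (1.50 at SD 2, 2.24 at SD 3).

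**5. Interval with arm, anxiety and pre-procedure pain in the model.** Take the case in which pre-procedure pain adds nothing. The residual SD is 2.5 × √(1 − r²). Estimating two slopes inflates the variance on average by 1 + 2/25 = 1.08 (the 25 is 30 − 5), and t has 26 degrees of freedom. Half-width, from the root-mean-square SE, = 2.056 × 2.5 × 0.365 × √1.08 × √(1 − r²) = 1.95 × √(1 − r²). This agrees with simulation of the same model.

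| r | √(1 − r²) | Half-width | Against 1.87 |
|---|---|---|---|
| 0.2 | 0.980 | 1.91 | about 2% wider |
| 0.3 | 0.954 | 1.86 | about 0.5% narrower |
| 0.5 | 0.866 | 1.69 | 10% narrower |
| 0.6 | 0.800 | 1.56 | 17% narrower |

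Break-even is at r = √[1 − (1.87/1.95)²] = 0.28.

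**6. Error rates.** In a simulation of 100,000 trials per value of r, the unadjusted test had an overall type I error of 5%. An imbalance above 0.5 anxiety SD arises in 17% of trials. Within those, the error was 7%, 12% and 18% at r = 0.3, 0.5 and 0.7. ANCOVA on anxiety alone stayed at about 5%.

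**7. Raw change in pain as an alternative.** Variance relative to the post score alone = (s_pre² + s_post² − 2ρ s_pre s_post) / s_post². With s_post = 2.5:
- s_pre = 1.5, ρ = 0.2: (2.25 + 6.25 − 1.5)/6.25 = 1.12.
- s_pre = 2.5, ρ = 0.1: (6.25 + 6.25 − 1.25)/6.25 = 1.80.

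If pre-procedure pain is weakly related to later pain, subtracting it adds 12% to 80% to the variance.

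**The case against.** **The plan is silent; it does not exclude adjustment.** This stands. A reader might infer that Section 11.2 adjusts pain for the wrong baseline, or commits to the raw change as its main pain result. The text supports neither: it names no adjustment, no change score and no main pain result. What can be said is that no use of anxiety is specified.

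**Randomisation already protects the comparison.** This stands on average. A reader might infer that the unadjusted difference is biased, or that an anxiety imbalance reappears in full as a pain difference. It does not: overall type I error is 5%, and the shift is scaled by r. The 0.3 to 0.5 points from a 1-point imbalance at r = 0.3 to 0.5 lie well inside a half-width of 1.87. What remains is lost precision, and error in the particular trial that happens to be imbalanced.

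**The correlation is unknown.** This stands. The description in Section 5.2 is narrative. The supporting study is in colposcopy, and its title in the reference list refers to state-trait anxiety, not to a single 0–10 item before MVA. A calculation that uses anxiety alone and ignores the cost of estimating slopes gives intervals 4%, 13% and 20% narrower at r = 0.3, 0.5 and 0.6. Those figures overstate what the two-covariate model delivers.

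**Pre-procedure anxiety may not be a true baseline.** This stands. If a woman already knows her arm when she scores her anxiety, allocation may have affected the score, and adjusting for it could remove part of the VR effect.

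**The missing between-arm comparison is the more basic gap, and this is a feasibility study.** Both are true. They limit the weight of the point but do not remove it. A between-arm comparison needs a stated model, and the covariates can be settled in the same sentence.

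**Conclusion.** The point holds as a modest improvement to the analysis of a secondary outcome. The protocol identifies anxiety as a strong influence on pain and collects it before the procedure, yet Section 11.2 specifies no use of it for pain. An unadjusted comparison would be valid on average, but it is exposed to imbalance: there is a 27% chance of a difference of at least 1 point, on an assumed anxiety SD of 2.5.

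The gain from adjustment depends on a correlation that the documents do not give. With an assumed pain SD of 2.5 and an uninformative pre-procedure pain score, it is nil or slightly negative at r of 0.3 or below, and about 10% to 17% of the interval width at r of 0.5 to 0.6. If pre-procedure pain is informative, the relevant r for anxiety is the partial correlation, and what anxiety itself adds may be smaller. The primary feasibility endpoint is not affected.

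**What to change.** In Section 11.2, state that post-procedure pain will be compared between arms by ANCOVA, with allocated arm, pre-procedure anxiety NRS and pre-procedure pain NRS as terms. The result should be reported as an adjusted difference with a 95% CI, in place of the raw pre-to-post change in pain. Show pre-procedure anxiety by arm in the baseline table.

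In Section 9, state that the pre-procedure questionnaire is completed before the woman learns her allocation, so that the anxiety score is a true baseline.

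The cost is two sentences and a fixed order for questionnaire and allocation at the clinic. No new data are needed. The model uses two of the 28 degrees of freedom, and the interval is slightly wider (about 1.91 against 1.87 at r = 0.2) if anxiety proves only weakly prognostic.
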